### Medical History

All clinically relevant medical history according to the investigator judgment will be captured in the appropriate eCRF.

### IRT

All patients that are screened must be registered with IRT. If the patient results in a screen failure, IRT should be notified as soon as possible and within the screening period. Details of IRT procedures can be found in the IRT manual located in the ISF.

### Re-screening

Patients who do not fulfil all eligibility criteria and are screen failed for a reason that later resolves and allows eligibility criteria to be met can be rescreened up to one time. For re-screening, patient must be re-registered in IRT, which will then provide new patient number, and patient must sign new Informed Consent Form (ICF). Imaging of retina (SD-OCT, OCTA, fundus photography) does not need to be repeated at the re-screening visit if the corresponding criteria for inclusion of the study eye were met at the initial screening visit and the images are not older than 28 days at the re-screening visit; otherwise new images have to be performed.

## **6.2.2 Treatment period(s)**

For the SRD part, masking is not required for the IVT injection preparation or administration. For the MD part, IVT injection will be prepared by the unmasked pharmacist (qualified person). For the MD part, an unmasked injector with no other involvement in the trial will administer either active or sham injection according to the treatment assigned by IRT. IVT injections must be carried out according to medical standards and applicable guidelines by a qualified physician experienced in administering IVT injections and will be done as part of drug administration visit procedures (Visit 2 for SRD part and Visits 2, 3 and 4 for MD part) after the other ophthalmologic assessments in the [Flow Chart I](#) and [Flow Chart II](#) have been performed (please see Section [4.1](#) for details).

## **6.2.3 Follow-up period and trial completion**

Patients must continue to be followed according to the visit schedule (unless they withdraw consent for further follow-up) in order to collect data at the end of the planned observation period. Unscheduled visits will be possible at the discretion of the investigator at any time for safety reason. The unscheduled visit may include any assessments considered necessary by the investigator. All unscheduled visits should be described and documented in the medical /source record. The investigator may decide other treatment options during the follow-up period as deemed medically appropriate.

### SRD part

#### Visit 8/End of Study:

The Visit 8/EOS will be performed 42 days after Visit 7 (see Flow Chart I).  
The Visit 8/EOS is the final visit and the End of Study CRF has to be completed.

### MD part

#### Visit 7/End of Study:

The Visit 7/EOS will be performed 42 days after Visit 6 (see [Flow Chart II](#)).  
The Visit 7/EOS is the final visit and the End of Study eCRF has to be completed.

### Withdrawal of consent

Every effort should be made to keep the patient in the trial and undergoing the procedures and follow up as outlined in the [Flow Charts I](#) and II and Section [6.2.3](#).

If a patient is not willing to continue in the trial and wants to withdraw consent prior to the end of the study, Visit 7 (SRD part)/ Visit 6 (MD part) should be scheduled as soon as possible, and also Visit 8/EOS(SRD part)/ Visit 7/EOS(MD part) should be performed to assess for safety.

The End of Study eCRF has to be filled in even if patient refuses to participate to the above specified visits.

For AE assessment, laboratory tests, recording of ECG and vital signs, and physical examination during the follow-up period, see Section [5.2](#).

Patients who discontinue treatment before the end of the planned treatment period should undergo the EOS Visit.

All abnormal values (including laboratory parameters) that are assessed as clinically relevant by the investigator will be monitored using the appropriate tests until a return to a medically acceptable level is achieved. (S)AEs persisting after a patient's EOS Visit must be followed until they have resolved, have been sufficiently characterised, or no further information can be obtained.

## 7. STATISTICAL METHODS AND DETERMINATION OF SAMPLE SIZE

### 7.1 STATISTICAL DESIGN – MODEL

This trial will consist of an SRD part followed by an MD part. The SRD part will be conducted non-randomized, open-label, and uncontrolled. MD part will be conducted single-blind, randomized and sham-controlled. The main objectives of this trial will be assessed by calculating descriptive statistics on DLEs and drug related AEs. For the MD part these will be compared descriptively between the treatment groups.

#### SRD part

The dose escalation will be guided by a Bayesian 2-parameter logistic regression model with overdose control [R13-4803, R13-4806]. For a given dose, the EWOC criterion is that there should be less than 25% risk that the true ocular DLE rate is above 0.25.

The model is given as follows:

$$\text{logit}(\pi_d) = \log(\alpha) + \beta \cdot \log(d/d^*),$$

where  $\text{logit}(\pi) = \log(\pi/(1-\pi))$ ,  $\pi_d$  represents the probability of having a DLE in the evaluation period at dose  $d$ ,  $d^* = \blacksquare$  is the reference dose, allowing for the interpretation of  $\alpha$  as the odds of a DLE at dose  $d^*$ , and  $\theta = (\log(\alpha), \log(\beta))$  with  $\alpha, \beta > 0$  is the parameter vector of the model.

The estimated probability of a DLE at each dose level from the model will be summarized using the following intervals:

Target toxicity: [0.00, 0.25)

Over toxicity: [0.25, 1.00]

The BLRM-recommended dose for the next cohort is the dose level with the highest posterior probability of the DLE rate falling in the target interval [0.00, 0.25) among the doses fulfilling EWOC. Thus, it should be unlikely (< 25% posterior probability) that the DLE rate at that dose will exceed 0.25. However, the allowed dose increment will always be the next higher pre-planned dose. However, the maximum allowable dose increment for the subsequent cohort will be no more than 250% from the previous dose. Dose escalation will continue up to the  $\blacksquare$  dose as long as the EWOC criterion for the next dose level is fulfilled. At the final dose, at least 6 treated patients are required. However, the SMC may decide to include additional number of patients at this dose level.

Since a Bayesian approach is applied, a prior distribution  $f(\theta)$  for the unknown parameter vector  $\theta$  needs to be specified. This prior distribution will be specified as a mixture of three multivariate normal distributions, i.e.

$$f(\theta) = a_1 f_1(\theta) + a_2 f_2(\theta) + a_3 f_3(\theta)$$

with  $a_i$ ,  $i = 1, 2, 3$  the prior mixture weights ( $a_1 + a_2 + a_3 = 1$ ), and  $f_i(\theta) = \text{MVN}(\mu_i, \Sigma_i)$ , the multivariate normal distribution of the  $i$ -th component with mean vector  $\mu_i$  and covariance matrix  $\Sigma_i$ , where

$$\Sigma_i = \begin{pmatrix} \sigma^2_{i,11} & \sigma_{i,11}\sigma_{i,22}\rho_i \\ \sigma_{i,11}\sigma_{i,22}\rho_i & \sigma^2_{i,22} \end{pmatrix}.$$

Mixture prior distributions have the advantage that they allow for specification of different logistic dose-toxicity curves, therefore making the prior more robust.

For the current study, no relevant information in the form of human data is available, since no study in a comparable population has been conducted. Therefore, the three mixture components were established as follows:

1. A weakly informative prior was derived reflecting the a priori assumption that the median DLE rate at the starting dose of ██████████ would equal 0.02, and the median DLE rate at the maximum feasible dose of ██████████ would equal 0.10. This yields  $\mu_1 = (-2.005 \ 0.0516)$ . The standard deviations were set such that large uncertainty about the parameter means is reflected, and the correlation was set to 0, thus yielding  $\sigma_{1,11} = 2$ ,  $\sigma_{1,22} = 1$  and  $\rho_1 = 0$ , respectively. The prior weight  $a_1$  for the first component was chosen as 0.9.
2. A high-toxicity weakly informative prior was derived reflecting the case that the compound would be much more toxic than expected. For this prior component, it was assumed that the median DLE rate at the starting dose of ██████████ would equal 0.15, and the median DLE rate at ██████████ would equal 0.40. These assumptions yield  $\mu_2 = (-0.255 \ -0.191)$ . The standard deviations and correlations were set identical to the weakly informative prior, i.e.  $\sigma_{2,11} = 2$ ,  $\sigma_{2,22} = 1$  and  $\rho_2 = 0$ , respectively. The prior weight  $a_2$  for the second component was chosen as 0.05.
3. A low-toxicity weakly informative prior was derived reflecting the case that the compound would be much less toxic than expected. For this prior component, it was assumed that the median DLE rate at the starting dose of ██████████ would equal 0.005, and the median DLE at ██████████ would equal 0.01. These assumptions yield  $\mu_3 = (-4.516 \ -0.835)$ . The standard deviations and correlations were set to  $\sigma_{3,11} = 5$ ,  $\sigma_{3,22} = 0.01$ , therefore almost fixing the slope parameter to its mean. The correlation was set to 0, i.e.  $\rho_3 = 0$ . The prior weight  $a_3$  for the third component was chosen as 0.05.

A summary of the prior distribution is provided in Table [7.1: 1](#). Additionally, the prior probabilities of DLEs at different doses, as well as the corresponding probability of targeted and overdosing, are shown in Table [7.1: 2](#). Graphically, the prior medians with accompanying 95% credible intervals are shown in Figure [7.1: 1](#). As can be seen from both Table [7.1: 2](#) and Figure [7.1: 1](#), the prior medians of the DLE probabilities are in line with the prior medians derived from the weakly informative prior, and the uncertainty around the medians is large, showing the low amount of information this prior provides. This is also supported by the prior sample size, i.e. the information contained in the prior. This is approximately equal to 1.7 patients. A detailed evaluation of the model using hypothetical data scenarios and operating characteristics is provided in Appendix [10.2](#).

Table 7.1: 1 Summary of prior distribution

Prior Component	Mixture Weight	Mean Vector	SD Vector
1: Weakly inf.	0.900	-2.005 0.0516	2.00 1.00
2: High Tox.	0.050	-0.255 -0.191	2.00 1.00
3: Low Tox.	0.050	-4.516 -0.835	5.00 0.01

Table 7.1: 2 Prior probabilities of DLEs at selected doses

Dose	Probability of true DLE rate		mean	sd	Quantiles		
	(0-0.25]	[0.25-1]			2.50%	50%	97.50%
0.5	0.883	0.117	0.091	0.170	0	0.013	0.703
1	0.836	0.164	0.121	0.201	0	0.025	0.775
2.5	0.714	0.286	0.202	0.245	0.001	0.092	0.880

[figure not shown]

Figure 7.1: 1 Prior medians and 95% credible intervals

The prior may be updated once the trial has started in case new data that can be used will be available. Only patients for which the occurrence of DLEs within the evaluation period can be evaluated will be considered. The prior that is used for each BLRM analysis for the SMC meetings will be documented in the SMC minutes, the prior used for the final analysis will be documented in the TSAP.

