##### SRD part:

In the SRD part, the starting dose is [REDACTED]. The other provisional dose level is [REDACTED], and the maximum planned dose is [REDACTED]. For each cohort, a single patient will be dosed on day 1, and the dosing investigator, coordinating investigator and 2 representatives of the sponsor who are involved in the trial will carefully evaluate all available systemic (i.e. physical examinations, safety lab parameters, ECG and AEs) and ophthalmologic (i.e. as defined in Section 5.2.1) safety data until day 4. If this patient neither has experienced an ophthalmologic nor a systemic serious adverse event, the remaining 2 patients will be dosed. Written minutes of this assessment are being distributed to all investigators participating in this trial.

For any dose-escalation cohort, at least 3 evaluable patients will be required. Each cohort will consist of newly enrolled patients.

A Safety Monitoring Committee (SMC, see Section 8.7) will decide on the next dose level to be investigated and on the size of the next cohort based on occurrence of DLEs and on additional information (systemic PK and patient profiles). Systemic PK data from preceding cohorts (not from the ongoing cohort) will be available for evaluation. First SMC meeting will take decision based on safety data only. Refer to figure 3.1:1 (SRD) and figure 3.1:2 (MD) for a schematic representation of the dose escalation.

A Bayesian logistic regression model (BLRM), based on a weekly informative prior distribution, and employing the escalation with overdose control (EWOC) principle (see Section 7) will be used for guiding the dose escalation [R13-4803]. After all patients in a cohort have either experienced a DLE or have been observed for at least the 7 days evaluation period without experiencing a DLE (I.e. 7 days after drug administration, until visit 4, will be evaluated per patient), the BLRM will be updated with the newly accumulated data. The overdose risk will then be calculated for each dose, and escalation will be permitted to all planned doses which fulfil the EWOC criterion and the respective escalation rule.

The BLRM provides estimates for the probability of observing a DLE for each planned dose. Dose escalation will be permitted to the next planned dose which fulfils the EWOC criterion. Note that this may also result in repeating the current dose level, or in going down to a lower dose level again.

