If DLEs are observed in the first two consecutive patients of a previously untested dose level, subsequent enrolment to that cohort will be stopped.

The maximum feasible dose (MFD) is considered as reached if at least 6 patients have been evaluated at a dose level which is the model's recommendation for the next dose cohort. Note the MFD will likely be the highest feasible dose, [REDACTED], rather than the highest tolerable dose in strict sense. The MD part of the study would only start if the highest dose ([REDACTED]) is tolerated.

- After the DLE period (7 days after drug administration) is over for the last patient in the SRD part, all available trial data will be analyzed and a decision is made whether to proceed to the MD part or not. Before starting the MD part, regulatory authorities and institutional review boards (IRBs) / independent ethics committees (IECs) will be informed of the internal results of the SRD part.

[figure not shown]

Figure 3.1: 1 Schematic representation of the dose escalation process in the SRD part of the trial

MD part:

The MD part will consist of one dose cohort (N=20 on dose + 10 sham injection). The highest dose [REDACTED] if established as safe and tolerable during the SRD part will be used in the MD part after the SRD part has been completed. Patients that had received a dose in the SRD part of the trial will not be included. Patients will be randomized to receive either active treatment or sham injection.

In the MD cohort, patients will receive three consecutive doses/sham injection over a 3-month period (dosing every 4 weeks). The SMC will meet regularly to review the safety data.

In all patients included in the MD part of the trial, safety and early biological response will be studied up to 98 days after the last injection.

[figure not shown]

Figure 3.1: 2                      Schematic representation of the dosing in the MD part of the trial

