## 7.7 DETERMINATION OF SAMPLE SIZE

### SRD part

No formal statistical power calculations to determine sample size were performed for this explorative study. A Bayesian logistic regression model (BLRM) was used for guiding the dose escalation process (see Section [3.1](#) for details). For the SRD part, a minimum of 3 patients and a maximum of 15 patients will be expected for this trial based on the number of dose levels/cohorts that are tested (for details regarding the BLRM assumptions refer to appendix [10.2](#)). Fewer patients might be needed based on the recommendation of the SMC. However, the actual number of patients will depend on the number of dose cohorts tested. Based on the simulation study to evaluate operating characteristics of the BLRM, about 15 evaluable patients are expected to be treated in the dose escalation part for the model to have reasonable operating characteristics relating to its MFD recommendation.

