### Hypothetical data scenarios

Hypothetical data scenarios are shown in Table 10.2: 1. These scenarios reflect potential on-study data constellations and related escalation as allowed by the model and the planned dose groups. It is assumed that each cohort has exactly three patients who are all evaluable. For each scenario, the probability of overdose for the current dose, as well as the next potential dose and related probabilities of target dosing and over-dosing are shown (probability of over-dosing: P(OD), probability of target dosing: P(TD)).

For example, scenario 1 represents the case that no DLE is observed in 3 patients at the starting dose of [REDACTED]. In this case, the next planned dose permitted by the model and the 200% escalation rule is [REDACTED]. In contrast, scenario 2 assumes that there is one DLE observed in the first dose group. This would mean over toxicity from the beginning, and the recommendation would be to stop the trial.

In scenario 3, there is no DLE after the first 2 dose groups, which would allow the trial to continue to the next dose level. If no further DLE occurs in the trial (scenario 6c), dose escalation would proceed to the [REDACTED] dose, with an additional cohort at that dose level at the end, i.e. overall 12 patients.

In scenario 4, the first DLE occurs in dose group [REDACTED]. Then the recommendation would be to treat an additional cohort of 3 patients at the same dose level. If no new DLE occurs then, scenario 4b shows that the next recommended dose level would be [REDACTED]. Thus, the [REDACTED] dose would be declared as MFD and the trial would stop (after 9 patients).

However, if (after repeating dose group [REDACTED] according to the recommendation from scenario 4) there was another DLE in the second cohort for dose group [REDACTED] (as in scenario 5), then the recommendation would be to go back to dose [REDACTED]. If there was no further DLE then (scenario 5b), the recommendation would be to go to next dose [REDACTED]. If there was no DLE in the third cohort of [REDACTED] (scenario 5c), then the trial would stop after 15 patients and declaring [REDACTED] as the MFD.

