### Operating characteristics

Operating characteristics are a way to assess the long-run behavior of a model by illustrating the precision of the design in estimating the MFD. Under an assumed true dose-toxicity curve, metrics such as the probability of recommending a dose with true DLE rate in the target interval can be approximated via simulation. Table [10.2: 2](#) describes 6 assumed true dose-toxicity scenarios which were used to assess the operating characteristics of the model. These scenarios reflect a wide range of possible cases as follows:

- Scenario 1: aligned with prior medians
- Scenario 2: aligned with prior means
- Scenario 3: high-toxicity scenario

- Scenario 4: low-toxicity scenario
- Scenario 5: non-logistic dose-toxicity scenario
- Scenario 6: low-toxicity followed by high-toxicity

Table 10.2: 2 Assumed true dose-toxicity scenarios

Scenario		Dose (mg)			
		■	■	■	■
1: Prior Med	P(DLE)	0.014	0.024	0.054	0.112
2: Prior Mean		0.086	0.106	0.153	0.224
3: High Tox		0.150	0.200	0.280	0.350
4: Low Tox		0.001	0.005	0.010	0.100
5: Non-Logistic		0.050	0.010	0.200	0.500
6: Low-High		0.010	0.050	0.400	0.600

For each of these scenarios, 1000 trials were simulated. Each cohort consisted of 3 patients and dose escalation complied with the following rule:

*Escalate to the maximum dose which satisfies the overdose criterion and is  $\leq 500\%$  increase from the current dose.*

The MFD was considered reached if at least 6 patients have been evaluated at a dose level which is the model's recommendation for the next dose cohort. The maximum allowed patient number for each trial was chosen as 24.

It was then assessed how often a dose was declared as MFD with true DLE rate in the targeted or in the overdosing range. Furthermore, the average, minimum and maximum number of patients per trial and the average number of DLEs per trial are reported. Results are shown in Table [10.2: 3](#).

Table 10.2: 3 Simulated operating characteristics

Scenario	Max. allowed # Patients	% of trials declaring a MFD with true DLE rate in		% of stopped trials*	# Patients	# DLEs
		[██████] target dosing	[██████] overdosing		Mean (Min-Max)	Mean (Min-Max)
1	15	94.1	0.0	5.9	11.8 (3-15)	0.39 (0-3)
2	15	65.4	0.0	34.6	9.1 (3-15)	1.10 (0-4)
3	15	23.8	13.6	62.6	8.5 (3-15)	1.88 (0-6)
4	15	100	0	0	9.2 (9-15)	0.06 (0-1)
5	15	67.9	0	32.1	10.7 (3-15)	1.16 (0-4)
6	15	47.9	20.3	31.8	13.1 (3-15)	2.01 (0-5)

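### Section 7.1's definition of the BLRM-recommended dose always picks the lowest EWOC-admissible dose, and the Section 10.2 simulations allow a dose skip that 7.1 forbids

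*Protocol*

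**What the plan says.** **The recommendation.** Protocol Section 7.1 (SRD part) uses two intervals for the DLE rate: target [0, 0.25) and over-toxicity [0.25, 1]. EWOC requires a posterior risk below 25% that the rate is above 0.25, and the slope β is positive. The model's recommendation is defined as follows: "the dose level with the highest posterior probability of the DLE rate falling in the target interval [0.00, 0.25) among the doses fulfilling EWOC". The same paragraph adds that "the allowed dose increment will always be the next higher pre-planned dose", caps the increment at 250%, and continues escalation to the top dose "as long as the EWOC criterion for the next dose level is fulfilled".

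**The MFD.** Section 3.1 states: "Dose escalation will be permitted to the next planned dose which fulfils the EWOC criterion". The MFD is reached once "at least 6 patients have been evaluated at a dose level which is the model's recommendation for the next dose cohort".

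**The appendix.** In the worked examples of Section 10.2, a trial without DLEs reaches the top dose "with an additional cohort at that dose level at the end, i.e. overall 12 patients", and the first example mentions a 200% rule. The simulations follow a different instruction, "Escalate to the maximum dose which satisfies the overdose criterion", with increases of up to 500% allowed. Section 7.7 relies on them: "about 15 evaluable patients are expected to be treated in the dose escalation part for the model to have reasonable operating characteristics".

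**The SAP.** The SAP text available does not restate the recommendation rule. Section 7 carries the protocol prior into the BLRM evaluations, and Section 7.4.1 reports counts and percentages of patients with DLEs.

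**The concern.** Choosing the dose with the most posterior mass in a target interval works when the interval has a lower bound, because doses that are too low are then penalised. Here every low DLE rate counts as on target, so the criterion never favours going up. Determining the MFD is the main objective (Section 2.1.1). The MFD is defined through the model's recommendation, and Section 7.1 is where that recommendation is defined.

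The simulations raise a second question. If they may skip a level that the design may not skip, the operating characteristics behind Section 7.7 describe a path the trial could not take.

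**Working it through.** **1. The sentence as a rule.** The two intervals are complementary, so P(target) = 1 − P(over). The model is logit(π_d) = log α + β·log(d/d*) with β > 0, so π_d increases with d for every parameter value. P(π_d < 0.25) therefore falls as d rises, and its maximum over the admissible doses is always at the lowest one. This needs no redacted figure.

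**2. The printed table shows the conflict.** In Table 10.2:1, scenario 1, the current dose has P(OD) 0.025, so P(target) = 1 − 0.025 = 0.975. The recommendation is 1 mg, with P(TD) 0.945. In scenario 3 the current dose has 1 − 0.016 = 0.984, and the recommendation is 2.5 mg with 0.874. Both move to the dose with the lower target probability.

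**3. Rebuilding the model.** Inputs:
- The three-component prior in Table 7.1:1.
- Doses 0.5, 1 and 2.5 from Table 7.1:2.
- The reference dose d*, which is redacted and was inferred. For component 1 at 0.5: logit(0.02) = −3.892 and β = exp(0.0516) = 1.053, so log(0.5/d*) = (−3.892 + 2.005)/1.053 = −1.792 and d* = 3.00. The other printed medians give 2.998 to 3.001.

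The posterior weight is the prior times Π π_d^r (1 − π_d)^(n − r), integrated numerically. Prior P(OD) comes out at 0.117, 0.162 and 0.290 (printed 0.117, 0.164 and 0.286). Table 10.2:1 reproduces within 0.006 except in rows 5b and 5c.

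**4. Both rules on Table 10.2:1.** The literal sentence gives 0.5 mg in all 13 rows that have a recommendation and agrees with the table once (scenario 5). The highest EWOC dose at most one level up agrees with all 14 rows, including no dose in scenario 2.

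**5. The SRD outcome.** Protocol Section 1.2 reports 12 treated patients and no DLE; SAP Section 6.1 gives 12 enrolled. With at least 3 per dose (Section 1.3) and at least 6 at the final dose (Section 7.1), the only split over three doses is 3/3/6. P(OD) is then 0.0002, 0.0007 and 0.013. The literal sentence recommends 0.5 mg, where 3 < 6 patients were treated, so the MFD criterion is met nowhere. The intended rule recommends 2.5 mg, with 6 patients there.

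**6. The skip.** Going from 0.5 to 2.5 is an increase of (2.5 − 0.5)/0.5 = 400%. That is inside the 500% rule, but outside both the one-level limit and the 250% cap. After 0/3 at 0.5 mg, P(OD) at 2.5 mg is 0.183 < 0.25, so the simulated trial takes the skip.

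Mean patients were computed by exact enumeration with cohorts of 3 and a maximum of 15. The first three redacted columns of Table 10.2:2 were taken as 0.5, 1 and 2.5. An MFD was declared when the current dose is recommended again with at least 6 patients there. SE is for 1000 trials.

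| Scenario | Printed | Skip | One level | Printed minus skip / one level, in SE |
|---|---|---|---|---|
| 1 | 11.8 | 9.6 | 11.8 | +28 / −0.4 |
| 2 | 9.1 | 9.1 | 9.9 | −0.3 / −5.7 |
| 3 | 8.5 | 8.4 | 8.2 | +0.6 / +1.9 |
| 4 | 9.2 | 9.2 | 12.0 | +1.2 / −112 |
| 5 | 10.7 | 10.8 | 11.7 | −0.5 / −8.3 |
| 6 | 13.1 | 13.1 | 12.6 | +0.1 / +6.6 |

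In scenario 4, 96.7% of trials end at 9 patients with the skip and 1.5% without it. Scenario 3's target/overdose percentages are printed as 23.8/13.6; the skip gives 20.2/21.2 and one level gives 31.3/12.1. Neither reproduces the split.

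**The case against.** The strongest reply is that the sentence should not be read alone. Section 3.1 gives a workable escalation rule, the 7.1 paragraph qualifies the sentence at once, and Table 10.2:1 shows the rule in use. The SMC chooses doses, the MD part starts on tolerability of the highest dose, and the planned SRD analysis is a DLE frequency table. All of this stands. A reader might infer that the escalation or the choice of 2.5 mg was unsound; the documents do not support that. They support only that the written definition is wrong and does not yield the MFD that the trial's data indicate.

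It might also seem that the 250% cap is idle and could go, since the planned steps are 100% and 150%. But Section 4.1.3 permits intermediate or lower dose levels. After an unplanned lower dose the cap can bind: from an illustrative 0.1 to 0.5 is +400%, which the next-planned-dose clause alone would allow.

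On the simulations, a reader might conclude that the operating characteristics are invalid or that the maximum of 15 is unsupported. That goes too far. One-level means run from 8.2 to 12.0 in scenarios 1 to 5 and reach 12.6 in scenario 6. The one-level rule gives lower overdose percentages than the skip (scenario 3: 12.1 against 21.2; scenario 6: 18.3 against 20.2). The appendix's view that the model is generally conservative survives.

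Target-MFD percentages need care, because they depend on the stopping condition. Requiring the current dose to be recommended again gives 69.1/70.6 (skip / one level) in scenario 5 and 46.2/53.2 in scenario 6. The plain wording of at least 6 patients at the recommended dose gives 84.4/85.7 and 75.1/77.9. The first condition lies nearer the printed 67.9 and 47.9, but the protocol does not state it.

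**Conclusion.** The point holds and should be fixed. The recommendation sentence in Section 7.1 is wrong as written, by an argument that needs no assumption about redacted values. It contradicts 12 of the 13 recommendations in Table 10.2:1, and through it the MFD criterion is met at no dose for 0/12 split 3/3/6, against 2.5 mg under the intended rule. That application assumes all 12 patients were evaluable. The intended rule is recoverable, so the consequence lies in the definition behind the main objective. Conduct, dose decisions and the DLE tables do not change.

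The simulation rule also conflicts with 7.1. Mean patient numbers in scenarios 2, 4, 5 and 6 fit the skip, scenario 1 fits only the one-level rule, and scenario 3's mean fits either while its target/overdose split fits neither. The increment rule therefore does not explain the whole table. The attribution of rows rests on the inferred d* = 3 and on the assumed dose columns; the effect is mainly on patient numbers.

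**What to change.** Replace the sentence in Section 7.1 with:

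> The BLRM-recommended dose for the next cohort is the highest dose under consideration (planned, or an intermediate or lower level agreed under Section 4.1.3) that fulfils EWOC, is at most one planned level above the current dose and is within the 250% increment cap; if no dose fulfils EWOC, none is recommended.

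Keep the target interval and the 250% cap, and align the 200% mention in Section 10.2 with the cap. Under Table 10.2:3, note that the simulations allowed a level to be skipped and that most rows' patient numbers reflect this, or rerun the six scenarios one level at a time. State the stopping condition with any target-MFD percentage. Report the MFD under the corrected rule.

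The cost is one sentence, one aligned figure and one note, or a rerun that takes little computing. Tables 7.1:2 and 10.2:1 are unaffected by the rule change. No new patient data are needed and, with recruitment complete, conduct does not change.
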